9.5.3 Bleeding and Spotting

Bleeding patterns will be analyzed using data from the subject diary. A cycle analysis and an analysis by RP will be performed (see Section 5.1.2 for details). Derived data for bleeding and spotting will be listed in the ITT Population.

9.5.3.1 Cycle Analysis

The cycle analysis will be performed following two approaches: a classical (for details see Section 5.10.2.2) and a modified cycle analysis (for details see Section 5.10.2.3).

The classical analysis will be performed in the ITT and PP Population. This analysis will also be repeated for the following populations:

- The PP analysis excluding cycles where there is at least 1 day where an active pill was missed
- The ITT analysis including only cycles where 1 active pill was missed
- The ITT analysis including only cycles where 2 or more active pills were missed.

The number of subjects with evaluable cycles for each population will be summarized by cycle.

The modified cycle analysis where early and continued withdrawal bleeding are classed as unscheduled bleeding will be performed in the ITT Population, PP Population and the PP Population excluding cycles where there is at least 1 day where an active pill was missed.

Details of the exclusion of cycles from the PP Population are provided in Section 5.1.2. Vaginal bleeding will be classified as spotting or bleeding and scheduled or unscheduled based on the definitions in Section 5.10.1 and 5.10.2. Rules for handling missing data are provided in Section 5.15.2. The inclusion of cycles in ITT Population, PP Population and PP Population excluding cycles with at least 1 active pill missed in the cycle will be listed by subject and cycle along with reasons for exclusion of the cycle from the PP Population analysis and the number of missed pills.

The following information will be summarized for bleeding and spotting for the cycle analysis:

- Number and percentage of subjects with unscheduled bleeding and/or spotting episodes for each cycle (classical analysis + modified cycle analysis)
- Number and percentage of subjects with unscheduled bleeding only episodes for each cycle (classical analysis + modified cycle analysis)
- Number and percentage of subjects with unscheduled spotting only episodes for each cycle (classical analysis + modified cycle analysis)
- Number and percentage of subjects with absence of a scheduled bleeding and/or spotting episode for each cycle (classical analysis + modified cycle analysis)
- Number and percentage of subjects with early withdrawal bleeding and/or spotting for each cycle
- Number and percentage of subjects with continued withdrawal bleeding and/or spotting for each cycle
- Number and percentage of subjects with absence of any bleeding and/or spotting for each cycle
- Descriptive statistics (e.g., mean, SD, median, minimum, and maximum) for the number of days of bleeding and/or spotting, bleeding only, and spotting only within a cycle for (classical and modified cycle analysis):
 - Total Days (Unscheduled + Scheduled)
 - Unscheduled Days
 - Scheduled Days

- Cumulative number and percentage of subjects with absence of withdrawal bleeding and/or spotting in the ITT Population only (classical analysis)
 - The number of subjects who have no withdrawal bleeding and/or spotting that started in at least 1 cycle, at least 2 cycles, at least 3 cycles and so on up to at least 13 cycles. The denominator is the number of subjects with at least 1 evaluable cycle, at least 2 evaluable cycles, at least 3 evaluable cycles and so on up to at least 13 evaluable cycles, respectively, for the specified population

Note that the denominator for the percentages listed above will be the number of subjects with an evaluable cycle unless otherwise specified.

The percentage of subjects with bleeding, the percentage of subjects with spotting and the percentage of subjects with absence of bleeding and/or spotting for each day will be presented in a bar chart over time for the ITT, PP Populations and Populations based on active pill counts. The plot will start on Day 4 of Cycle 1 because Days 1-3 of Cycle 1 are not assigned to a shifted cycle so cannot be assigned to the specified analysis populations. The 3 days imputed for the days included in shifted Cycle 13 after Day 28 of Cycle 13 in the diary will not be included in the plot as these do not reflect the true bleeding pattern. Day will be the day from the diary data i.e. pill intake days (examples: Day 4 = Cycle 1 Day 4 or Day 118 = Cycle 5 Day 6). The denominator will be the number of subjects with an evaluable cycle for the specified population on that day.

The descriptive statistics (e.g., mean, SD, median, minimum, and maximum) for the number of unscheduled bleeding and/or spotting days, bleeding days, and spotting days within a cycle will also be summarized in subjects who experienced an unscheduled bleeding and/or spotting episode within that cycle. This will be presented for the classical and modified analysis in the ITT and PP Populations. Additionally, unscheduled bleeding and spotting and the absence of scheduled bleeding will be summarized for all subgroups specified in Section 4.3 by cycle for the classic cycle analysis for the ITT, PP Population and the PP Population excluding cycles with at least 1 missed active pill and the modified cycle analysis for the ITT Population.

The number and percentage of subjects with a scheduled bleeding episode starting on each day in the scheduled bleeding period in the shifted cycle (i.e. Day 25, 26, 27, 28 and Day 1, 2 and 3 of the next cycle in the diary) will be summarized by Cycle. If there is more than one scheduled bleeding episode, then the only the earliest start date of the scheduled bleeding episodes starting within the cycle will be counted. This will be presented for the classical and modified analysis in the ITT Population.

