5.10.2 Cycle analysis

5.10.2.1 Definition of cycles

In the cycle analysis of a 24/4 regimen of a COC, an up to 7-day vaginal bleeding is scheduled to occur in conjunction with the first inactive tablet (Day 25) and end on Day 3 of the next cycle (expected bleeding period). In principle, no vaginal bleeding is expected to occur at other times during the cycle. This means that the remainder of the cycle constituted the expected non-bleeding period of 21 days. Therefore, any bleeding/spotting that occurs during the expected non-bleeding period (starting on Day 4 of the actual cycle up to and including Day 24) are considered as unscheduled.

The following definitions (**Table 2**) will be used for the cycle analysis:

Table 2: Bleeding/spotting definitions used for the cycle analysis

Scheduled Bleeding/Spotting (Withdrawal Bleeding/Spotting)	Any bleeding/spotting that occurs during the hormone-free interval (i.e. Days 25 – 28) and continues through Days 1-3 of the subsequent active cycle. Note: any bleeding/spotting that occurs while taking active hormones during Days 1-7 of the first cycle will be imputed as no bleeding.
Unscheduled Bleeding/Spotting	Any bleeding/spotting that occurs while taking active hormones that does not meet the criteria for scheduled bleeding/spotting.
Unscheduled Bleeding	Any bleeding that occurs while taking active hormones that does not meet the criteria for scheduled bleeding.
Unscheduled Spotting	Any spotting that occurs while taking active hormones that does not meet the criteria scheduled spotting.
Early Withdrawal Bleeding/Spotting	Any bleeding/spotting episode that starts before the scheduled bleeding/spotting period and continues into the scheduled bleeding/spotting period.
Continued withdrawal bleeding/spotting	Any bleeding/spotting episode that starts in the scheduled bleeding/spotting period and continues after the scheduled bleeding/spotting period.

Based on these definitions, the cycle analysis of bleeding/spotting episodes will perform in two ways:

- a classical approach
- a modified cycle analysis

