5.10.2.2 Classical cycle analysis

In the classical analysis, early and continued withdrawal bleeding are regarded as scheduled.

The following rules will be used for the classical approach to classify each bleeding only episode, spotting only episode or bleeding/spotting episode as scheduled or unscheduled:

The episode is defined as unscheduled, if any of the following criteria are met:

- The episode has a start date after Day 7 of Cycle 1 and an end date that is on or before Day 24 of Cycle 1
- For Cycles 2 to 13, the episode has a start date after Day 3 of the cycle and an end date that is on or before Day 24 of the cycle

The episode is defined as scheduled (withdrawal bleeding and/or spotting), if any of the following criteria are met:

- The episode has a start date after Day 24 of the cycle and an end date that is on or before Day 3 of the next cycle
- The episode has a start date after Day 24 of the cycle and an end date that is after Day 3 of the next cycle (continued withdrawal bleeding/spotting).
 - Note it is not possible to have continued withdrawal bleeding for Cycle 13 because data are not collected for Cycle 14
- The episode has a start date before Day 24 of the cycle and an end date on or after Day 25 (early withdrawal bleeding/spotting).

All bleeding days and spotting days will then be classified as scheduled or unscheduled based on whether the bleeding or spotting days are included in a scheduled or unscheduled episode using the rules in this Section above. A bleeding day or spotting day that occurs in a scheduled episode will be classified as scheduled and a bleeding day or spotting day that occurs in an unscheduled episode will be classified as unscheduled.

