5.10.2.3 Modified Cycle Analysis

In the modified cycle analysis, the definitions of expected non-bleeding and expected bleeding periods are strictly followed, i.e., all bleeding episodes that overlap with expected non-bleeding intervals are considered unscheduled. Thus in this analysis, the definitions of scheduled and unscheduled bleeding/spotting episodes presented in the Table 2 are also applicable, but early and continued withdrawal bleedings are regarded as unscheduled.

Therefore, in the derivation of endpoints where early and continued withdrawal bleeding are classed as unscheduled bleeding the following rules are used to classify each bleeding only episode, spotting only episode or bleeding/spotting episode as scheduled or unscheduled:

The episode is defined as unscheduled, if any of the following criteria are met:

- The episode has a start date after Day 7 of Cycle 1 and an end date that is on or before Day 24 of Cycle 1
- For Cycles 2 to 13, the episode has a start date after Day 3 of the cycle and an end date that is on or before Day 24 of the cycle
- The episode has a start date after Day 24 of the cycle and an end date that is after Day 3 of the next cycle (continued withdrawal bleeding/spotting)
 - Note it is not possible to have continued withdrawal bleeding for Cycle 13 because data are not collected for Cycle 14
- The episode has a start date before Day 24 of the cycle and an end date that is on or after Day 25 (early withdrawal bleeding/spotting)

The episode is defined as scheduled (withdrawal bleeding and/or spotting), if the following criterion is met:

• The episode has a start date after Day 24 of the cycle and an end date that is on or before Day 3 of the next cycle

All bleeding days and spotting days will then be classified as scheduled or unscheduled based on whether the bleeding or spotting days are included in a scheduled or unscheduled episode in the same way as outlined for the classical analysis but using the rules in this Section above where early and continued withdrawal bleeding are classed as unscheduled episodes.

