5.10.4 Bleeding Endpoints for the Cycle Analysis

For the cycle analysis, the evaluable cycles will be determined as described in Section 5.1 for each subject, missing data rules are provided in Section 5.15.2 and definitions of terminology are provided in Section 5.10.1 and 5.10.2.

Depending on the approach used for the cycle analysis (the classical approach versus the modified cycle analysis), for each evaluable cycle for each subject, the following will be determined:

• Whether there was at least one unscheduled bleeding only, spotting only or bleeding/spotting episode within that cycle (see Section 5.10.2 for definition). It will be assumed that there is at least

one unscheduled episode during the cycle if there is an unscheduled episode that starts in the cycle of interest

- Whether there was at least one unscheduled bleeding only episode within that cycle (see Section 5.10.2 for definition) and no unscheduled bleeding/spotting episodes and no unscheduled spotting only episodes. It will be assumed that there is at least one unscheduled bleeding only episode during the cycle if there is an unscheduled bleeding only episode that starts in the cycle of interest
- Whether there was at least one unscheduled spotting only episode within that cycle (see Section 5.10.2 for definition) and no unscheduled bleeding/spotting episodes and no unscheduled bleeding only episodes. It will be assumed that there is at least one unscheduled spotting only episode during the cycle if there is an unscheduled spotting only episode that starts in the cycle of interest
- Whether there is an absence of any bleeding or spotting (i.e. all days in the cycle are bleeding/spotting-free days)
- Whether there is an absence of scheduled bleeding only, spotting only and bleeding/spotting episodes (i.e. there is no scheduled episode with a start date during that cycle of interest)
- Whether there is early withdrawal bleeding or spotting in that cycle (i.e. there is either an early withdrawal bleeding only, spotting only or bleeding/spotting episode that starts during the cycle of interest)
- Whether there is continued withdrawal bleeding or spotting in that cycle (i.e. there is either a continued withdrawal bleeding only, spotting only or bleeding/spotting episode that starts during the cycle of interest)

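### The modified cycle analysis reports a withdrawal bleed that crosses the window boundary as absence of scheduled bleeding, and an episode starting on Day 24 fits neither rule

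*SAP*

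**What the plan says.** SAP 5.10.2.1 splits the 28-day cycle into an expected bleeding period, from Day 25 to Day 3 of the next cycle, and an expected non-bleeding period, from Day 4 to Day 24. It treats "any bleeding/spotting that occurs during the expected non-bleeding period" as unscheduled. Table 2 in the same section describes scheduled bleeding by the same days.

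Two analyses follow. SAP 9.5.3.1 puts it this way: "The cycle analysis will be performed following two approaches: a classical (for details see Section 5.10.2.2) and a modified cycle analysis". They differ on episodes that cross the edge of the window:

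- 5.10.2.2: "In the classical analysis, early and continued withdrawal bleeding are regarded as scheduled".
- 5.10.2.3: "all bleeding episodes that overlap with expected non-bleeding intervals are considered unscheduled". The Table 2 definitions are said to remain applicable, "but early and continued withdrawal bleedings are regarded as unscheduled".

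In both sections the early-withdrawal criterion requires a start before Day 24 and an end on or after Day 25. Every day takes the label of its whole episode.

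SAP 5.10.4 then defines absence of scheduled bleeding for either approach: "there is no scheduled episode with a start date during that cycle of interest". SAP 9.5.3.1 tabulates that absence by cycle under both approaches. The modified analysis "will be performed in the ITT Population, PP Population and the PP Population excluding cycles where there is at least 1 day" with a missed active pill. Absence of scheduled bleeding is also summarised by subgroup, and the modified analysis supplies the ITT version of those subgroup tables.

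**The concern.** The modified rule is presented as a strict reading of the expected bleeding and non-bleeding periods. For deciding whether an episode was purely a withdrawal bleed, it is a usable label. The difficulty comes when the label is carried into the absence endpoint. A reader takes that endpoint to say whether the woman had her expected bleed. Under the modified rule, a woman who bled through most of the window but started a few days early or ran one day over has no scheduled episode, and is counted with women who did not bleed at all.

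Cycle control is the first of the other secondary objectives (SAP 2.3), and absence of scheduled bleeding is one of the two bleeding outcomes selected for subgroup analysis in SAP 4.3. An absence rate that mixes late-ending bleeds with true amenorrhoea could mislead about the product and about differences between subgroups.

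The Day 24 gap is a smaller drafting defect. Table 2 describes early withdrawal bleeding as starting before the scheduled period, which would include Day 24. The operative criteria in 5.10.2.2 and 5.10.2.3 leave Day 24 out.

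**Working it through.** **Windows (SAP 5.10.2.1).** Non-bleeding period: 24 − 4 + 1 = 21 days, as the SAP states. Bleeding period: (28 − 25 + 1) + 3 = 7 days. Total 28. The plan's figures reproduce.

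**Single episodes, each the only one in its cycle.**

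| Episode | Days | In window | Classical | Modified | Absence, classical | Absence, modified |
|---|---|---|---|---|---|---|
| Day 26 to next Day 2 | 5 | 5 | scheduled | scheduled | no | no |
| Day 27 to next Day 4 | 6 | 5 | scheduled (continued) | unscheduled | no | **yes** |
| Day 20 to Day 26 | 7 | 2 | scheduled (early) | unscheduled | no | **yes** |
| Day 24 to Day 27 | 4 | 3 | no criterion met | no criterion met | **yes**, read literally | **yes**, read literally |

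The last row fails each test in turn. It ends after Day 24, so it is not unscheduled by the within-cycle criterion. It does not start after Day 24, so it is neither scheduled nor continued. It does not start before Day 24, so it is not early. With no scheduled label it counts as absence under both approaches.

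**All patterns.** Take every episode of 1 to 14 days that starts between Day 4 and Day 3 of the next cycle: 28 × 14 = 392 start and length pairs.

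- Early (start before Day 24, end on or after Day 25): 78.
- Continued (start in the window, end after next Day 3): 70.
- Start on Day 24 and run into Day 25 or later: 13.
- Total crossing a boundary: 78 + 70 + 13 = 161.

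In all 78 + 70 = 148 early or continued pairs there is at least one bleeding day in the window, yet the modified rule yields no scheduled episode. The 13 Day 24 pairs are unclassified under either rule. Pairs that do not cross a boundary are labelled alike by both rules. These are counts of patterns, not of women.

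**Size.** Let a be the share of cycles without scheduled bleeding under the classical rule, and f the share with an early or continued bleed. The modified absence rate is at most a + f. It is lower if a cycle also contains a separate episode wholly inside the window. Protocol 7.2 gives a Phase 2 withdrawal bleeding rate of 96.5%, so a = 100 − 96.5 = 3.5%, used only as an illustrative base because its definition may differ. No document gives f.

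| Assumed f | Modified absence, at most |
|---|---|
| 2% | 5.5% |
| 5% | 8.5% |
| 10% | 13.5% |
| 20% | 23.5% |
| 30% | 33.5% |

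Simulating one withdrawal bleed per cycle does not narrow this. With mean start Day 26 (SD 1) and mean length 4 days (SD 1), about 11% of cycles are reported as absent under the modified rule; about 6 of those 11 points are Day 24 starts. With mean starts of Day 26 to 27 (SD 1 to 1.5) and mean lengths of 4.5 to 5.5 days (SD 1.3 to 1.8), the figure runs from 18% to 55%. The result is driven by the assumed start day and length, which the documents do not supply.

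**The case against.** The best defence is that the reader is not left without help. SAP 12.1 records that the classical definition is the primary one and the modified is not. The classical absence row is printed as well, and the cumulative absence table is classical ITT only. SAP 9.5.3.1 tabulates early and continued withdrawal bleeding by cycle, which are the episodes that change class, and plots bleeding for each diary day. The row is titled as absence of a scheduled episode, which is literally what it counts, and absence of any bleeding has its own row. All of this is descriptive. These points stand, and they limit the harm. They do not make the modified absence row correct, and the listed subgroup outputs cover unscheduled bleeding and absence of scheduled bleeding without an early or continued breakdown.

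Three stronger readings are tempting, and the documents do not support them.

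- A reader might infer eight rival estimates with no main one. The count is right: "The classical analysis will be performed in the ITT and PP Population. This analysis will also be repeated for the following populations" gives five classical cycle sets, and the modified analysis adds three. But 12.1 already ranks the two rules, and the sets restricted by missed pills are compliance breakdowns, not competing headlines. What is missing is a statement in 9.5.3.1 and a named main set.
- A reader might infer that episode-based day counts are an error because they depart from Days 4 to 24. The departure arises only for boundary-crossing episodes, and 12.1 records the move to episode-based days as a deliberate change. Replacing it would leave open which cycle the days belong to, since 5.10.4 assigns them to the cycle in which the episode starts. It would also clash with the 9.5.3.1 summary of unscheduled days, which is restricted to subjects with an unscheduled episode.
- A reader might quote the upper simulated figures as the expected distortion. They rest on assumed bleeding patterns and, in part, on Day 24 starts that the written rules do not classify.

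**Conclusion.** The point holds in a limited form. The modified absence endpoint gives a wrong result by its own stated rule: it reports no scheduled bleeding for a woman who bled on up to all 7 days of the expected window, whenever the episode also extends outside it. Each early or continued withdrawal bleed inflates the modified absence rates unless another episode lies wholly inside the window. In Cycle 13 only early bleeds can do so, because 5.10.2.3 rules out continued ones there. The Day 24 omission is a separate gap that affects both approaches.

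The direction is certain, but the size is not known from the documents; the figures shown are conditional on assumed frequencies or bleeding patterns. No contraceptive efficacy or safety result is touched. The protocol's own table of bleeding definitions (section 12.6.1) was not in the text available for review, so the SAP rules could not be compared with it.

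**What to change.** 1. In SAP 5.10.4 and 9.5.3.1, define absence of scheduled bleeding, in both approaches, as no bleeding or spotting day from Day 25 to Day 3 of the next cycle. The shifted cycle used for the bleeding analysis already contains this whole window, so no new rule is needed for assigning days to cycles.
2. In 5.10.2.2 and 5.10.2.3, change the early-withdrawal criterion so that it covers a start on or before Day 24.
3. Keep the episode-based labels and day counts, which are a documented choice.
4. Optional: add a supportive row of unscheduled days counted by calendar position (Days 4 to 24), and carry the 12.1 statement that the classical definition is primary into 9.5.3.1, with ITT named as the main set.

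The cost is SAP wording and a small derivation change on diary data already collected. The absence row becomes the same under both approaches, so the modified version no longer adds information. The classical row should hardly move.

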9.5.3.2 Reference Period Analysis

All RP analysis will be performed in the ITT Population only. The following information will be summarized for bleeding and spotting for the **RP analysis**:

- Descriptive statistics (e.g., mean, SD, median, minimum, and maximum) for the number of days of bleeding and/or spotting, bleeding only, and spotting only within a RP.
- Descriptive statistics for the number of bleeding and/or spotting episodes in each RP
- Descriptive statistics for the mean duration of the bleeding and/or spotting episodes in each RP
- Descriptive statistics for the number of bleeding and/or spotting free episodes in each RP
- Descriptive statistics for the mean duration of the bleeding and/or spotting free episodes in each RP

Note that the denominator for the percentages listed above will be the number of subjects with an evaluable RP.

The number of subjects with evaluable reference periods for each population will be summarized by reference period. The inclusion of reference periods in ITT Population will be listed by subject and reference period along with reasons for exclusion of the reference period.

